8.2.2 Allowed Concomitant Medications/ Treatments/ Procedures

Subjects who are taking antibiotic eye drops or ointments or non-preserved artificial tears for at least two weeks at the time of screening may continue to use them throughout the study at the discretion of the Investigator. However, these medications should not be started after the subject begins the study.

If a subject is taking one of the above listed allowed concomitant eye drops or ointments during the study the subject should be instructed to dose with the study eye drops first and wait at least 5 minutes before dosing with the other medication.

The use of these medications will be collected and recorded in the concomitant medications page of the eCRF.

8.2.3 Escape Medications

At the discretion of the investigator, subjects may use topical steroid as an escape medication. Subjects receiving the escape medications will be exited, and will be counted as subjects who did not have complete healing of the epithelial defect in the primary efficacy analysis.

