
Study Formulations and Formulation Numbers:
	
Study Drug:                  RGN-259 Ophthalmic Solution (and Placebo) to be supplied by ReGenTree.

Evaluation Criteria:
	

Efficacy Measures:
	
Primary Efficacy Measures:                  Percentage of subjects achieving complete healing of the persistent epithelial defect as determined by corneal fluorescein staining at 4 weeks (Visit 5).
 
Secondary Efficacy Measures:
 
 
• Percentage of subjects achieving complete healing of the persistent epithelial defect determined by corneal fluorescein staining at Visits 2, 3, 4, 6, and 7;
 

	

• Epithelial Defect Measurement and Classification at Visits 2, 3, 4, 5, 6, and 7;

• Tear Film Break-up Time at Visits 5, 6, and 7;

• Ocular Discomfort using Ora Calibra™ Discomfort and 4-Symptom Questionnaire at Visits 2, 3, 4, 5, 6, and 7;

• Visual Acuity at Visits 2, 3, 4, 5, 6, and 7.

Safety Measures:	

• Visual Acuity (ETDRS);

• Slit-Lamp Biomicroscopy;

• Cochet-Bonnet;

• Adverse Event Query;

• Dilated Fundoscopy;

• Intraocular Pressure.

General Statistical Methods and Types of Analyses Analysis Populations: 

• [REDACTED]

 Sample Size: Primary Efficacy Analysis:	

[REDACTED]

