## 4 OVERALL STUDY DESIGN

This is a Phase 3, multicenter, randomized, double-masked study designed to evaluate the efficacy and safety of RGN-259 ophthalmic solution compared to placebo in patients with neurotrophic keratopathy. Approximately 46 male and female patients at least 18 years of age with stage 2 or stage 3 neurotrophic keratopathy (Mackie Classification) and meeting all other study eligibility criteria will be randomized to receive treatment with [REDACTED]. This study will consist of two periods: a 28-day treatment period and a 14-day post-treatment period. A study flow chart appears below:

Patients who terminate early during the treatment period or post-treatment period will be asked to complete safety assessments. Patients who are terminated early from the study will not be replaced.

In this study, the vehicle of RGN-259 ophthalmic solution has been selected as the placebo control to objectively evaluate the efficacy and safety of RGN-259 ophthalmic solution. In addition, randomized assignment and double-masked design features have been implemented to minimize any bias for patient selection and data evaluation.

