8.2.4 Escape Surgical Intervention

At the discretion of the investigator, subjects may undergo surgical intervention (ex. tarsorrhaphy, amniotic membrane graft) to address their persistent epithelial defect. Subjects receiving surgical intervention will be exited, and will be counted as subjects who did not have complete healing of the epithelial defect in the primary efficacy analysis.

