### 9.9 Statistical Hypothesis and Sample Size

H0: There is no difference between study eyes treated with RGN-259 and study eyes treated with placebo, RGN-259 – placebo, in the percentage of study eyes achieving complete healing of epithelial defect at Day 29 (Visit 5).

HA: There is a difference between study eyes treated with RGN-259 and study eyes treated with placebo, RGN-259 – placebo, in the percentage of study eyes achieving complete healing of epithelial defect at Day 29 (Visit 5).

The study will be considered a success if H0 is rejected in favor of HA [REDACTED]  
[REDACTED]

[REDACTED]

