9.1 Unit of Analysis

The unit of analysis in this study will be the study eye for all efficacy summaries and any treated eye for ocular safety summaries. In general, NK is unilateral. If a patient presents with bilateral epithelial defects that both meet the entry criteria, the study eye will be defined as the affected eye with the largest affected area, and the other eye will be considered a qualified fellow eye. If both affected eyes have the same affected area, the right eye will be the study eye and the left eye will be considered a qualified fellow eye.

Ocular AEs will be summarized for all eyes and for any treated eye (if at least one subject has bilateral NK in which both eyes are treated), and ocular safety assessments will be analyzed by study eye and both treated eyes (again, if at least one subject has bilateral NK in which both eyes are treated), where the worst safety outcome over both eyes is summarized. Medical history and non-ocular AEs and safety assessments will be presented at the subject level.

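### Could escape treatment after Visit 5, or only in the fellow eye, turn an observed Day 29 success into a failure?

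*Protocol*

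**What the plan says.** Two clinical sections carry the scoring rule. On steroid, Protocol 8.2.3 says that subjects given it as escape leave the study and "will be counted as subjects who did not have complete healing of the epithelial defect in the primary efficacy analysis". On surgery, Protocol 8.2.4 says: "Subjects receiving surgical intervention will be exited, and will be counted as subjects who did not have complete healing of the epithelial defect". Surgery is described as being done "to address their persistent epithelial defect"; the steroid section gives no such tie.

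The primary hypothesis (Protocol 9.9, repeated in SAP 3.4) concerns a difference "in the percentage of study eyes achieving complete healing of epithelial defect at Day 29 (Visit 5"). Protocol section 4 divides the study into "a 28-day treatment period and a 14-day post-treatment period", so subjects are observed for two weeks after the endpoint is read. SAP 9.1 makes the study eye the unit for efficacy. In a bilateral case where both eyes qualify, "the other eye will be considered a qualified fellow eye". The same section says the disease is usually on one side.

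The detailed text on unit of analysis, missing data and the primary analysis is redacted in the protocol (9.10.2 to 9.10.4). So are SAP 9.2 and the methods text of SAP 14.1. SAP section 1 says its methods replace those of the protocol.

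**The concern.** The escape rule is written for the subject and has no end date; the endpoint belongs to one eye on one day. Taken word for word, two kinds of event could reverse a success already observed at Visit 5: escape between Day 29 and Day 43, and escape given only for the fellow eye. The primary outcome would then mix Day 29 healing with later or unrelated events. If healed subjects in both arms were rescored at the same rate, the arm with more healed eyes would lose more successes and a true difference would shrink. In a trial this small, a single rescored subject can move a result across the 5% line.

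**Working it through.** **1. Nothing to reproduce.** The healing rates, alpha, allocation ratio and dropout behind the sample size are redacted. The arithmetic below is illustrative and assumes 1:1 allocation, a two-sided Fisher exact test at 5%, and true Day 29 healing of 60% on active and 20% on placebo.

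**2. Weight of one subject.** One rescored success moves an arm's healing rate by 100/n points:
- N = 46 (Protocol 5.1): 100/23 = 4.3 points
- N = 42 (SAP 6.1): 100/21 = 4.8 points
- N = 18 (SAP 4.3): 100/9 = 11.1 points

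This can decide a borderline result. At 23 per arm, 12 versus 4 healed gives p = 0.029, and 11 versus 4 gives p = 0.057. At 9 per arm, 6 versus 1 gives p = 0.0498, and 5 versus 1 gives p = 0.131.

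**3. Dilution.** Let q be the share of Day 29 successes rescored in each arm. The healed proportion becomes p(1 − q), and the difference becomes (1 − q) × (0.60 − 0.20).

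| q | Active | Placebo | Difference | Fisher power, 23 per arm |
|---|---|---|---|---|
| 0 | 0.60 | 0.20 | 0.40 | 0.727 |
| 5% | 0.57 | 0.19 | 0.38 | 0.682 |
| 10% | 0.54 | 0.18 | 0.36 | 0.637 |
| 20% | 0.48 | 0.16 | 0.32 | 0.549 |

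At 9 per arm, power is 0.279 with q = 0 and 0.227 with q = 10%. If the drug affects neither healing nor escape, rescoring lowers both arms alike and does not favour active.

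**4. What q could be.** The documents give no rate of escape among healed subjects. Subjects whose defect has closed are plausibly the least likely to need it. Surgery would require a recurrence in the study eye or a defect in the other eye.

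**5. What q was, on the documents' account.** Three statements bear on this:
- Protocol 8.2.3 and 8.2.4: anyone given escape treatment is exited.
- Protocol 8.6.1: a completer is someone who was not discontinued.
- SAP 4.3: 18 subjects enrolled, and these subjects completed.

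If SAP 4.3 uses the word as 8.6.1 defines it, the number exited is 18 − 18 = 0. No success was rescored, q = 0, and a narrower rule would return the same counts.

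**The case for a change.** The strongest counter-argument is that nothing visible narrows the rule. SAP section 18 plans no departure from the protocol's analyses, and SAP 4.3 says they proceed as first intended. One sentence would settle the matter at almost no cost. The sponsor also means to judge clinical relevance rather than significance, so an 11-point shift in an arm of 9 would matter even without a p-value.

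Part of this stands. The two sections do omit the time window and the eye, and the timing gap is the more real of the two. The eye gap matters mainly for steroid and only in bilateral cases.

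The rest does not carry. Section 18 cannot show that a limit is absent, because redacted protocol text could already contain it and no deviation would then be needed. The escape sections are silent on period; they do not say that the rule runs past Visit 5. Exiting the subject and scoring a failure appear in one sentence, which fits a rule for people who leave before the primary assessment and so have no Visit 5 value. An analyst working to a study-eye, Day 29 endpoint would apply it that way. A subject exited before Visit 5 for fellow-eye escape would have no Visit 5 value to protect. That case belongs to the missing-data rules, which are redacted.

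**Conclusion.** The wording is looser than it should be, but it calls for no change. It leaves a detail that analysts would fill sensibly from the stated endpoint, and filling it formally gains nothing here. The expected effect on the primary result is zero, provided that SAP 4.3 means completion in the sense of Protocol 8.6.1 and that exit for escape counts as discontinuation. The documents do not report the number of escapes directly, so this is an inference from those sections. The illustrated losses of 9 points of power at q = 10% (0.727 to 0.637) and 18 points at q = 20% (0.727 to 0.549) depend on assumed healing rates and on escape rates that have no source in the documents. With equal rates in both arms, the direction would be towards a smaller difference. It is not shown that any Day 29 success is overwritten in the primary analysis.

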8.2.4 Escape Surgical Intervention

At the discretion of the investigator, subjects may undergo surgical intervention (ex. tarsorrhaphy, amniotic membrane graft) to address their persistent epithelial defect. Subjects receiving surgical intervention will be exited, and will be counted as subjects who did not have complete healing of the epithelial defect in the primary efficacy analysis.

8.2.5 Special Diet or Activities

No special diets or activities are required for this study.

**8.3 Examination Procedures**

8.3.1 Procedures to be Performed at Each Study Visit with Regard to Study Objective(s)

**Visit 1 (Day 1): Screening/Enrollment/Baseline**

The following procedures will be performed:

- [REDACTED]
- [REDACTED]
- [REDACTED]
- [REDACTED]  
[REDACTED]
- [REDACTED]
- [REDACTED]
- [REDACTED]

- [REDACTED]
- [REDACTED]
- [REDACTED]
- [REDACTED]
- [REDACTED]  
[REDACTED]
- [REDACTED]
- [REDACTED]
- [REDACTED]  
[REDACTED]  
[REDACTED]  
[REDACTED]
- [REDACTED]  
[REDACTED]  
[REDACTED]
- [REDACTED]
- [REDACTED]
- [REDACTED]

**Visit 2 (Day 8 ± 2): One-Week Follow-Up**

The following procedures will be performed:

- [REDACTED]
- [REDACTED]
- [REDACTED]
- [REDACTED]  
[REDACTED]
- [REDACTED]
- [REDACTED]
- [REDACTED]  
[REDACTED]

- [REDACTED]
- [REDACTED]
- [REDACTED]
- [REDACTED]
- [REDACTED]
- [REDACTED]
- [REDACTED]

**Visit 3 (Day 15 ± 2): Two-Week Follow-Up**

The following procedures will be performed:

- [REDACTED]
- [REDACTED]
- [REDACTED]
- [REDACTED]
- [REDACTED]
- [REDACTED]
- [REDACTED]
- [REDACTED]
- [REDACTED]
- [REDACTED]
- [REDACTED]
- [REDACTED]
- [REDACTED]
- [REDACTED]

■ [REDACTED]

**Visit 4 (Day 22 ± 2): Three-Week Follow-Up**

The following procedures will be performed:

- [REDACTED]
- [REDACTED]
- [REDACTED]
- [REDACTED]  
[REDACTED]
- [REDACTED]
- [REDACTED]
- [REDACTED]  
[REDACTED]
- [REDACTED]  
[REDACTED]
- [REDACTED]  
[REDACTED]  
[REDACTED]
- [REDACTED]  
[REDACTED]  
[REDACTED]
- [REDACTED]  
[REDACTED]  
[REDACTED]
- [REDACTED]
- [REDACTED]
- [REDACTED]

**Visit 5 (Day 29 ± 2): Four-Week Follow-Up**

The following procedures will be performed:

- [REDACTED]
- [REDACTED]
- [REDACTED]
- [REDACTED]

- [REDACTED]
- [REDACTED]
- [REDACTED]
- [REDACTED]
- [REDACTED]
- [REDACTED]
- [REDACTED]
- [REDACTED]
- [REDACTED]
- [REDACTED]
- [REDACTED]

**Visit 6 (Day 36 ± 3): One-Week Post-Treatment Follow-Up**

The following procedures will be performed:

- [REDACTED]
- [REDACTED]
- [REDACTED]
- [REDACTED]
- [REDACTED]
- [REDACTED]
- [REDACTED]
- [REDACTED]
- [REDACTED]
- [REDACTED]

**Visit 7 (Day 43 ± 3): Two-Week Post-Treatment Follow-Up**

The following procedures will be performed:

- [REDACTED]

- [REDACTED]
- [REDACTED]
- [REDACTED]
- [REDACTED]
- [REDACTED]
- [REDACTED]
- [REDACTED]
- [REDACTED]
- [REDACTED]
- [REDACTED]
- [REDACTED]
- [REDACTED]
- [REDACTED]
- [REDACTED]

Adverse Events (both elicited and observed) will be monitored throughout the study. All adverse events (both elicited and observed) will be promptly reviewed by the Investigator for accuracy and completeness. All adverse events will be documented on the appropriate Source Document and electronic case report form (eCRF).

If a female has a positive pregnancy test during the study, then the Investigator will notify Ora immediately. The Investigator shall request from the subject and/or the subject's physician copies of all related medical reports during the pregnancy and shall document the outcome of the pregnancy. The Investigator will retain these reports together with the subject's source documents and will provide a copy of all documentation to Ora.

## **8.4 Schedule of Visits, Measurements and Dosing**

### 8.4.1 Scheduled Visits

[REDACTED]

### 8.4.2 Unscheduled Visits

[REDACTED]

- [REDACTED]
- [REDACTED]
- [REDACTED]
- [REDACTED]
- [REDACTED]
- [REDACTED]
- [REDACTED]
- [REDACTED]
- [REDACTED]
- [REDACTED]
- [REDACTED]
- [REDACTED]

#### 8.4.3 Early Termination Visits

These visits will be performed for any subject that is discontinued from the study prior to completion (for reasons listed in Section 8.6.2). All procedures performed at an early termination visit will be recorded in the source documents and on the appropriate eCRF pages. Any procedure indicated in the eCRF that is not performed should be indicated as “Not done.”

Evaluations that may be conducted at an Early Termination Visit include:

- [REDACTED]
- [REDACTED]
- [REDACTED]
- [REDACTED]
- [REDACTED]
- [REDACTED]
- [REDACTED]
- [REDACTED]
- [REDACTED]
- [REDACTED]
- [REDACTED]

#### 8.5 **Compliance with Protocol**

Subjects will be instructed on proper instillation and storage of study drug at the end of Visits 1, 2, 3, and 4 and given written instructions. Study

drug will be collected at each visit up to and including Visit 5 to assess dosing compliance. Dosing compliance will be based on the used vial count. If the subject uses [REDACTED] study drug during a dosing period, a subject will be deemed non-compliant and a dosing deviation will be recorded. These guidelines will be used by the Investigator for determining the subject's necessary compliance for the study and for recording deviations from this compliance.

## **8.6 Subject Disposition**

### **8.6.1 Completed Subjects**

A completed subject is one who has not been discontinued from the study.

### **8.6.2 Discontinued Subjects**

Subjects may be discontinued prior to their completion of the study due to:

- subject no longer willing to comply with study protocol;
- adverse events;
- protocol violations;
- lack of efficacy;
- administrative reasons (e.g. inability to continue, lost to follow-up);
- Sponsor termination of study;
- any sound medical reason in the Investigator's opinion.

Notification of a subject discontinuation and the reason for discontinuation will be made to Ora, Inc. and/or ReGenTree and will be clearly documented on the eCRF.

## **8.7 Study Termination**

The study may be stopped at any time by the Investigator, ReGenTree, and/or Ora with appropriate notification.

## **8.8 Study Duration**

An individual subject's participation will involve 7 visits over approximately a 6-week period.

## **8.9 Monitoring and Quality Assurance**

During the course of the study an Ora, Inc. will make routine site visits to review protocol compliance, ensure subject safety, assess study drug accountability, and ensure the study is being conducted according to the pertinent regulatory requirements. The review of the subjects' medical records will be performed in a manner that adequately maintains subject confidentiality. Further details of the study monitoring will be outlined in a monitoring plan.

Regulatory authorities of domestic and foreign agencies, Ora, Inc. Quality Assurance, ReGenTree, and/or its designees may carry out on-site inspections and/or audits which may include source data checks. Therefore direct access to the original source data will be required for inspections and/or audits. All inspections and audits will be carried out giving consideration to data protection as well as subject confidentiality to the extent that local, state, and federal laws apply.

## **9 ADVERSE EVENTS**

### **9.1 Adverse Event**

An adverse event (AE) is defined as any untoward medical occurrence associated with the use of an investigational medicinal product (IMP) in humans, whether or not considered IMP-related. An AE can be any unfavorable and unintended sign (e.g., an abnormal laboratory finding), symptom, or disease temporally associated with the use of an investigational product, without any judgment about causality. An AE can arise from any use of the investigational product (e.g. off-label use, use in combination with another drug or medical device) and from any route of administration, formulation, or dose, including an overdose.

All AEs spontaneously reported by the subject and/or in response to an open question from study personnel or revealed by observation, physical examination or other diagnostic procedures will be recorded in the source document and on the appropriate sections of the eCRF. Any clinically relevant deterioration in clinical finding is considered an AE and must be recorded. When possible, signs and symptoms indicating a common underlying pathology should be noted as one comprehensive event.

Documentation regarding the AE should be made as to the nature, date of onset, end date, severity, and relationship to investigational product, action(s)

taken, seriousness, and outcome of any sign or symptom observed by the physician or reported by the patient upon indirect questioning.

#### 9.1.1 Severity

Severity of an AE is defined as a qualitative assessment of the degree of intensity of an AE as determined by the Investigator or reported to him/her by the patient/subject. The assessment of severity is made irrespective of relationship to investigational product or seriousness of the event and should be evaluated according to the following scale:

- *Mild*: Event is noticeable to the subject, but is easily tolerated and does not interfere with the subject's daily activities.
- *Moderate*: Event is bothersome, possibly requiring additional therapy, and may interfere with the subject's daily activities.
- *Severe*: Event is intolerable, necessitates additional therapy or alteration of therapy, and interferes with the subject's daily activities.

#### 9.1.2 Relationship to Investigational Product

The relationship of each AE to the investigational product should be determined by the investigator using these explanations:

- *Definite*: When there are good reason and sufficient documentation to demonstrate a direct causal relationship between investigational product and AE;
- *Probable*: When there are good reasons and sufficient documentation to assume a causal relationship in the sense of plausible, conceivable, likely but not necessarily highly probable.
- *Possible*: When there is sufficient information to accept the possibility of a causal relationship in the sense of not impossible and not unlikely, although the connection is uncertain or doubtful, for example; due to missing data or insufficient evidence.
- *None*: When there is sufficient information to accept a lack of a causal relationship, in the sense of impossible and improbable.
- *Unclassified*: When the causal relationship is not assessable for whatever reason due to insufficient evidence, conflicting data or poor documentation.

#### 9.1.3 Expectedness

The expectedness of an AE should be determined based upon existing safety information about the investigational product using these explanations:

- *Unexpected:* an AE that is not listed in the Investigator's Brochure (IB) or Report of Prior Investigations (ROPI) or is not listed at the specificity or severity that has been observed.
- *Expected:* an AE that is listed in the IB or ROPI at the specificity and severity that has been observed.
- *Not applicable:* an AE unrelated to the investigational product.

Adverse events that are mentioned in the IB as occurring with a class of products or as anticipated from the pharmacological/ mechanical (or other) properties of the product, but are not specifically mentioned as occurring with the particular product under investigation are to be considered unexpected.

The Investigator should initially classify the expectedness of an AE, but the final classification is subject to the Medical Monitor's, ReGenTree's, and Ora's determination.

## 9.2 Serious Adverse Events

An AE is considered serious if, in the view of either the Investigator or Sponsor, it results in any of the following outcomes:

- Death;
- A life-threatening AE;
  - Note: An AE is considered "life-threatening" if, in the view of either the Investigator or Sponsor, its occurrence places the patient or subject at immediate risk of death. It does not include an AE that, had it occurred in a more severe form, might have caused death.
- Inpatient hospitalization or prolongation of existing hospitalization;
  - Note: The term "inpatient hospitalization" refers to any inpatient admission (even if less than 24 hours). For chronic or long-term inpatients, inpatient admission includes transfer within the hospital to an acute/intensive care inpatient unit. Inpatient hospitalization does not include: emergency room visits; outpatient/same-day/ambulatory procedures; observation/short stay units; rehabilitation facilities; hospice facilities; nursing homes; or clinical research/Phase 1 units.
  - Note: The term "prolongation of existing hospitalization" refers to any extension of an inpatient hospitalization beyond the stay anticipated or required for the reason for the initial admission as determined by the Investigator or treating physician.

- A persistent or significant incapacity or substantial disruption of the ability to conduct normal life functions;
  - Note: A serious AE (SAE) specifically related to visual threat would be interpreted as any potential impairment or damage to the subject's eyes (eg, hemorrhage, retinal detachment, central corneal ulcer or damage to the optic nerve).
- A congenital anomaly/birth defect.

Important medical events that may not result in death, are life-threatening, or require hospitalization may be considered serious when, based upon appropriate medical judgment, they may jeopardize the patient or subject and may require medical or surgical intervention to prevent one of the outcomes listed in this definition.

